9.1 Determination of Sample Size

a. Introduction and background

The sample size is computed on the primary outcome: SRTs measured in a 2 by 2 factorial design:

- 2 different test setups, talker from the side vs. from the back,
- 2 test conditions, R-BF vs. I-BF.

Traditional power analysis packages or software are unable to compute sample size calculation analytically for a two-way repeated measures design. Green & MacLeod (2016) and Kumle et al. (2021) propose an alternative power analysis based on simulations for a generalized (linear) mixed-effect model.

Mixed-effect models should be preferred over analysis of variance (Oleson et al., 2019) as it makes no assumption about the distribution of the outcome variable (only residuals should be independent and identically distributed) or sphericity (correlation between repeated measures) and allows to include random slopes in the model, assuming the fixed effects are not constant across tested subjects.

b. Principle of power analysis based on simulation

The principle for simulation-based power analysis is to 1) simulate a new dataset, 2) analysis each set and test for significance, and 3) calculate the proportion of significant to all simulations. The simulation of new data set is not trivial as it will affect the accuracy of the simulation. One possible way to generate the new data-set is to use an existing data-set from a well powered study. The power will be computed based on the reference data set in order to detect an a priori determined fixed effect, also described as the smallest effect size of interest (SESOI).

c. Reference data set

The reference data set is taken from Latzel & Appelton (2015) who measured SRTs with different beamformers (including the R-Bf and the I-BF) and 2 test setups with different spatial configurations (noise from around vs side). Individual data from this reference study are available and show interesting properties, as the experiment was conducted on 20 hearing aid users with the same range of hearing loss degree (moderate to severe) at the same investigation site. While these test setups have always the talker in front, these data provide valuable information about within subject variance with hearing aid users. The reference analysis is based on a linear mixed-effect model is fitted with setup, device, and interactions as fixed effect and subject as random factor with device as

random slope. The fixed effects are sum coded to get estimate of test setup and device that are easily interpreted.

The estimated effects are:

- test setup effect -0.6 dB SNR in average with a standard error of 0.2 dB SNR,
- device effect -3.0 dB SNR in average with a standard error of 0.4 dB SNR,
- interaction setup by device -1.6 dB SNR in average with a standard error of 0.4 dB SNR.

The effects of talker location and directional microphone are in line with data from Giuliani & Brayda (2019) who report SRTs measured with a single talker from different azimuth (from the back and the side) and different beamformers. While the test was performed with a different population (normal hearing listeners), different beamformers (virtual reality glasses) and test material (SRT in Italian with the Bocca test), the effects are similar with the reference data i.e., a decrease of 0.5 dB SNR when the talker is in the back instead of the side, a decrease of 4.5 dB SNR for the wider beamformer compared to narrower one, and a negative interaction of 0.5 dB SNR.

Results from both studies are consistent in direction even if there are some differences in their amplitudes. These observations are providing enough confidence for the simulation and we can therefore estimate the power based on the reference data for different sample sizes.

d. Simulation

We will make use of the mixed power function from the mixedpower package (Kumle et al., 2018, version 0.1.0) with varying sample size, since we want to compute the power for different sample sizes. The following simulation is based on 1000 runs with a varying sample size from 16 to 28. This range of sample sizes is usually reported in published articles about the effect of directional microphones and is also acceptable from a time and resources perspective.

Simulation is repeated two times. First on original data set where simulations rely on the same effect size provided by the reference model, which might be overpowered for the device effect. This increases the risk to perform analysis with inflated effect sizes and limit the chance of reproducing the results. The alternative is to specify the smallest effect size of interest (SESOI).

Specifying SESOI makes “it possible to design studies which are worthwhile to run, as they have a predetermined power to detect an effect that is of interest” (Albers & Lakens, 2018; Kumle et al., 2021). However, prior knowledge is required to specify an effect size of interest. The SESOI for the test device will be set to 1 dB SNR difference between both tested conditions. The choice of this SESOI is based on a study review and experience from previous studies. The other SESOI are averaged between both reference studies i.e., -0.6 dB for the setup and -1.0 dB for the interaction.

e. Sample size

The power for different sample sizes is shown by fixed effect in following figure:

A sample size of 20 subjects might be sufficient to detect a difference of 1.0 dB SNR between both beamformer conditions with a power of 80%. The research question for the study focuses on the effect of the beamformer so that the decision is based on this main effect only. The sample size will be extended by 10 % to 22 participants as there is a risk of drop out during a clinical investigation with multiple visits over a longer time frame.

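### Does the stated 80% power for a 1.0 dB beamformer difference with 20 participants conflict with the printed standard error of 0.4 dB?

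*Combined protocol and SAP*

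**What the plan says.** Section 9.1 a states the basis of the calculation: "The sample size is computed on the primary outcome: SRTs measured in a 2 by 2 factorial design", the factors being talker position and beamformer. Section 9.1 c takes the variability from an existing study, "who measured SRTs with different beamformers (including the R-Bf and the I-BF) and 2 test setups with different spatial configurations", and describes its size: "as the experiment was conducted on 20 hearing aid users with the same range of hearing loss degree". The mixed model fitted to those data gave three estimates. The one that matters most here is the "device effect -3.0 dB SNR in average with a standard error of 0.4 dB SNR". For the setup the model gave −0.6 dB (standard error 0.2), and for the interaction −1.6 dB (standard error 0.4).

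Section 9.1 d describes the power calculation: "The following simulation is based on 1000 runs with a varying sample size from 16 to 28". It was run once with the reference effects and once with a smallest effect of interest, set at 1 dB for the device. Section 9.1 e refers to a figure of power by sample size (not visible in the text available here), concludes that "20 subjects might be sufficient to detect a difference of 1.0 dB SNR between both beamformer conditions with a power of 80" percent, and adds 10% for dropout to reach 22.

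Elsewhere, section 6 (Oldenburg Sentence Test) has every beamformer-by-location cell measured at visit 1 and again at visit 2. Section 9.3.2 b puts a test-retest sequence term in the primary model, with a random beamformer slope and a likelihood ratio test for each fixed effect. Testing is two-sided at 0.05.

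**The concern.** The reference study had 20 users and the planning case is also 20. The printed device standard error can therefore be carried straight over: a true 1.0 dB difference has an expected test statistic of 1.0/0.4 = 2.5. That falls short of 80% power under any two-sided 5% criterion. The gap of about 11 points under the planned test is well beyond the error of a 1000-run simulation.

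The sizing text also never mentions the retest, so a reader cannot tell whether the simulated design is the one to be run. The trial is called confirmatory, and this one figure is the whole justification for its size. If the printed standard error were exact, the chance of missing a real 1.0 dB benefit would be about 25% at n=20 with the retest, not the 20% implied.

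**Working it through.** **Inputs.** Section 9.1: n=20 in the reference study; standard errors 0.2 (setup), 0.4 (device) and 0.4 (interaction); effect 1.0 dB. Section 9.3.2: two-sided 0.05, likelihood ratio test. Section 6: two runs per cell.

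**Assumptions.** The reference fit had two devices and one run per cell. The retest halves the residual variance. The beamformer effect does not vary by session within a participant.

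**1. Is 0.4 the standard error of the full beamformer difference?** With half-unit sum coding, the squared standard errors are:

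- setup: σ²/n
- interaction: 4σ²/n
- device: (τ² + σ²)/n, where τ² is the variance of the random beamformer slope

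The interaction standard error should then be twice the setup one. With ±1 coding the two would be equal. The printed ratio is 0.4/0.2 = 2, and rounding allows 0.35/0.25 = 1.4 to 0.45/0.15 = 3.0, which excludes 1. So 0.4 is the standard error of the full difference.

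**2. Variance components at face value.**

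- σ² = 20 × 0.2² = 0.8 from the setup line, and 20 × 0.4²/4 = 0.8 from the interaction line. The two agree.
- τ² = 20 × 0.4² − 0.8 = 2.4.

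**3. Power at face value.** With r runs per cell, SE = √((2.4 + 0.8/r)/n). The likelihood ratio test rejects when n·log(1 + t²/(n−1)) > 3.841, that is |t| > 2.006 at n=20 and 2.002 at n=22.

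| Design | SE | 1.0/SE | Likelihood ratio | t | Normal |
|---|---|---|---|---|---|
| 2 by 2, n=20 | 0.400 | 2.50 | 69.0% | 66.0% | 70.5% |
| 2 by 2, n=22 | 0.381 | 2.62 | 73.1% | 70.6% | 74.6% |
| With retest, n=20 | 0.374 | 2.67 | 74.5% | 71.8% | 76.2% |
| With retest, n=22 | 0.357 | 2.80 | 78.5% | 76.2% | 80.0% |

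The plan's 80% at n=20 is not reproduced at exactly 0.400.

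**4. Rounding.** A device standard error printed as 0.4 lies between 0.35 and 0.45. From the interaction line, σ² lies between 5 × 0.35² = 0.61 and 5 × 0.45² = 1.01. Likelihood ratio power then ranges over:

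- 2 by 2, n=20: 59% to 80%
- retest, n=20: 62% to 88%
- retest, n=22: 67% to 91%

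**5. What the 80% implies at n=20.** Power is exactly 80% at a device standard error of 0.349 (likelihood ratio) or 0.357 (normal) for the 2 by 2. With the retest and σ² = 0.8 the values are 0.377 or 0.384.

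The 95% simulation error is 1.96 × √(0.8 × 0.2/1000) = 0.025, so a reported 80% is compatible with a true 77.5%. The limits then become 0.361 or 0.368 (2 by 2) and 0.387 or 0.394 (retest). All four lie inside the rounding interval.

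**6. Direction of the retest.** Leaving the retest out of the simulation would understate power: 74.5 − 69.0 = 5.5 points at the printed values.

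**The case for a change.** The best case for a change is that the sizing section describes only a 2 by 2. For that layout under the planned test, 80% is reached only at the most favourable edge of the rounding interval (79.8% at 0.35). At the printed standard errors, likelihood ratio power first reaches 80% at n=26 without the retest and n=23 with it. The 78.5% at n=22 needs every participant to complete, whereas the two extra places are there to cover dropout. A rerun on data the sponsor already holds would cost little.

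The arithmetic stands, as does the remark that a reader cannot reproduce the figure. The inference to an error does not. The one-decimal standard errors summarise the reference fit; the simulation used the individual data behind them. Its test criterion is not stated in the visible text, and the power figure, which covers sample sizes from 16 to 28, cannot be seen here. That figure may already show power near n=22, and its absence from the extracted text does not count against the plan.

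The missing mention of the retest is weak evidence that it was omitted: section 9.3.2 b also calls the design 2 by 2 and then models test-retest in the same paragraph. Nor do the documents give the runs per cell in the reference data or say whether other beamformers entered the fit. If the reference data already had two runs per cell, the retest adds nothing over them, and the face-value figures are 69.0% (n=20) and 73.1% (n=22).

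**Conclusion.** No change to the plan follows. At a device standard error of exactly 0.400, power for 1.0 dB is about 69% (2 by 2, n=20), 74.5% (retest, n=20) and 78.5% to 80.0% (retest, all 22 completing). These figures rest on rounded inputs, two devices and one run per cell in the reference fit, and a retest that halves the residual variance.

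The stated 80% at n=20 requires an unrounded standard error of about 0.36 or less for the 2 by 2, or about 0.39 or less with the retest, allowing for simulation error. The printed 0.4 permits both. It equally permits lower power, so the documents neither confirm nor refute the figure, and the plan's own wording for n=20 is tentative.

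What is missing is reporting detail: the unrounded device standard error and variance components, the simulation's test criterion, and whether the retest was simulated. These would make a reasonable clarification query. Supplying them would alter neither the number enrolled nor the primary model nor how its result is read. If the retest was left out, that omission makes the stated power conservative.

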9.2 Statistical criteria of termination of trial

The clinical investigation is done under the constant supervision of the investigator in a controlled acoustical environment so that there is no suspicion of an unacceptable risk. There are therefore no statistical criteria who should justify the premature termination of the trial.

9.3 Planned Analyses

The statistical analysis plan includes the methods and types of the analysis, the variables the data sets and the timeframe when the (interim) analysis is planned.

9.3.1 Datasets to be analyzed, analysis population

Statistical analysis will be based on the per-protocol (PP) population. The PP population will include all participants with associated primary and secondary outcome data, excluding subjects who were deemed ineligible following screening visit, those who withdrew from the trial and were unwilling for their previously collected data to be utilized or those who failed to provide baseline.

9.3.2 Primary Endpoint Analysis

All the statistical tests will be performed at two-sided $\alpha=0.05$ if not specified differently. All reported p-values greater than or equal to 0.001 will be rounded to three decimal places and p-values less than 0.001 will be displayed as "<0.001". The analysis will be run using the statistical software R, version 4.1.1 (2021) (R Core Team 2021). The statistical analysis report will be written in a Rmarkdown format and exported into an HTML document.

a) Demographic Data

The following demographic and baseline characteristics will be tabulated overall for PP population: Age (years), 4-frequency Pure Tone Average (in dB HL), and case history i.e., hearing loss onset, otalgia, otorrhea, otitis, tinnitus.

For continuous variables (e.g., age) descriptive statistics will be presented (mean, interquartile range, and number of participants with data). For categorical variables frequencies, percentages and number of participants with data will be presented. The denominator for the percentages will be the number of patients with non-missing data.

b) Primary outcome: SRT for directional benefit

The SRT is a continuous variable expressed as the signal-to-noise ratio (in dB) necessary to achieve 50% intelligibility of the presented sentences. The SRT is measured in a 2 by 2 factorial design: talker factor (from the side or from the back) and beamformer (R-BF or I-BF). These SRTs will be analyzed with a linear mixed effect model with sequence (test-retest), talker location, beamformer, and interaction between location and beamformer as fixed effects. Participants will be treated as random factor with beamformer as random slope. The fixed effects are sum coded to get estimate of talker position and beamformer that are easily interpreted. The distribution of residuals will be visually checked to be independent and identically distributed. A likelihood ratio test will be made to obtain a p-value for each fixed effect.

c) Secondary outcome: listening effort for directional benefit

The listening effort is measured in dB SNR for three effort rating: no effort (1), moderate effort (7), and extreme effort (13). Lower SNRs indicate that the participant can tolerate more noise for the same subjective rating and stand therefore for better results. The ACALES results are measured with 2 talker locations, 2 beamformer settings, and twice (test-retest). Listening effort will be analyzed with a linear mixed effect model with sequence (test-retest), talker location, beamformer, and rated effort as fixed effects. Participants will be treated as random factor with beamformer as random

slope. The fixed effects are sum coded to get estimate of talker position and beamformer that are easily interpreted. The distribution of residuals will be visually checked to be independent and identically distributed. A likelihood ratio test will be made to obtain a p-value for each fixed effect.

d) Secondary outcome: listening effort for SE benefit

The ACALES will be repeated for 3 distances and 2 conditions (SE Off vs On). The outcome is a rating on a 13 points scale, as the difficulty is fixed by the distance now. The outcome is discrete and bounded at both ends so that a non-parametric test should be applied. Wilcoxon signed rank test will be made for each distance and Bonferroni correction for multiple comparison will be made for the three distances.

e) Secondary outcome: speech test for SE benefit

Word recognition is measured in percent for 2 conditions (SE Off vs On) and in two independent setups: 4 m distance and talker in adjacent room. Percent scores will be converted to arcsin units (Sherbecoe & Studebaker, 2004) for variance normalization. A paired t-test will be made for each condition, as the test setups address different and unrelated listening conditions.

f) Secondary outcome: subjective assessment questionnaire.

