(1) to evaluate whether I-BF provides better SRTs in noisy situation with speech from side and behind than with the R-BF with hearing impaired listeners (moderate to severe hearing loss) during a lab test session. Expected SRT improvement based on previous data is about 1 dB SNR with the I-BF and SRTs are measured with the OLSA test. Tested null hypothesis: there is no difference between the RBF and the I-BF.

Secondary objective for the beamformer benefit part is

(2) to evaluate whether I-BF provides less listening effort in noisy situation with speech from side and behind than with the R-BF with hearing impaired listeners (moderate to severe hearing loss) during a lab test session. Tested null hypothesis: there is no difference between the R-BF and the I-BF measured with the ACALES test with varying SNR.

Secondary objectives for the Speech Enhancer benefit part are:

(3) to evaluate whether the investigational device with Speech Enhancer activated provides less listening effort than without speech enhancer for distant speech in a quiet listening situation for people with moderate to severe hearing loss. Tested null hypothesis: there is no difference between Speech Enhancer activated or not measured with the ACALES test with varying distance.

(4-a) to evaluate whether the investigational device with Speech enhancer activated provides better speech intelligibility than without speech enhancer for distant speech in a quiet situation for people

with moderate to severe hearing loss. Tested null hypothesis: there is no difference between Speech Enhancer activated or not measured with the WaKo Rhyme Test.

(4-b) to evaluate whether the investigational device with Speech enhancer activated provides better speech intelligibility than without speech enhancer for speech from an adjacent room in a quiet situation for people with moderate to severe hearing loss. Tested null hypothesis: there is no difference between Speech Enhancer activated or not measured with the WaKo Rhyme Test.

(5-a) to evaluate whether the investigational device with Speech enhancer activated provides better subjective speech intelligibility and less listening effort than without speech enhancer for distant speech in a quiet situation without access to visual cues for people with moderate to severe hearing loss. Tested null hypothesis: there is no difference between Speech Enhancer activated or not with the subjective assessment questionnaire.

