The clinical investigation shall provide data to confirm the superiority of the I-BF over the RBF in listening situations where the dominant talker is not located in the front of the hearing aid user. These data shall be used as input for further product improvement and more efficient use of existing feature.

The clinical investigation shall provide data to confirm the superiority of the Speech Enhancer in communication situations with a distant talker. These data shall be used as evidence for further marketing communications and more efficient use of existing feature.

Better perception in different situations has been identified as one of the key elements to provide satisfaction to the hearing aid users (Picou, 2020). Therefore, the overall risk/benefit ratio is considered to be acceptable for this clinical investigation.

6 Endpoints

1) Oldenburg Sentence Test: Speech reception threshold (SRT)

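### Does averaging the beamformer effect over side and back talkers leave the primary conclusion unsupported when the two locations differ?

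*Combined protocol and SAP*

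**What the plan says.** Objective 1 (section 2) is "to evaluate whether I-BF provides better SRTs in noisy situation with speech from side and behind than with the R-BF". The null hypothesis attached to it is that "there is no difference between the RBF and the I-BF", with no location named. Section 5 describes the intended superiority conclusion as applying in "listening situations where the dominant talker is not located in the front of the hearing aid user".

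The primary analysis (section 9.3.2 b) is a "linear mixed effect model with sequence (test-retest), talker location, beamformer, and interaction between location and beamformer as fixed effects", with participant as random factor and beamformer as random slope. On coding and testing it says "The fixed effects are sum coded to get estimate of talker position and beamformer that are easily interpreted" and "A likelihood ratio test will be made to obtain a p-value for each fixed effect".

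Section 9.1 d plans for a 1 dB beamformer difference, a 0.6 dB setup effect and a 1.0 dB interaction. Section 9.1 e bases the sample size of 20 (22 with the allowance for drop-out) on the beamformer main effect alone, because that effect is the research question. Section 6 has every location-by-beamformer cell measured twice, at visits 1 and 2.

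**The concern.** A sum-coded main effect beside an interaction is an average. Benefits of 2 and 0 dB give the same main-effect estimate, and the same power, as 1 and 1 dB. A significant average therefore cannot by itself show that I-BF helps both from the side and from behind, yet Objective 1 names both positions. The interaction p-value says whether the two benefits differ, not whether either exceeds zero.

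The planning values make the issue concrete, because the assumed interaction (1.0 dB) is as large as the assumed main effect (1.0 dB). The plan does not say that location estimates or intervals will be reported, or how a significant interaction limits the conclusion. At stake is the wording of the main result: a benefit concentrated at one talker position could be presented as a benefit at both.

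**Working it through.** **Inputs.** Section 9.1 c: reference study of 20 users; standard errors 0.2 dB (setup), 0.4 dB (device) and 0.4 dB (interaction). Section 9.1 d: main effect 1.0 dB, interaction 1.0 dB. Section 9.1 c also gives the one source that compared side with back talkers, which reports "a negative interaction of 0.5 dB SNR". Section 9.3.2: two-sided 0.05.

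**The plan's own figure.** Power = Φ(1.0/SE − 1.96).
- SE 0.40: Φ(0.54) = 70.5%.
- Rounding limits of that SE: 0.35 gives 81.5%, 0.45 gives 60.3%.
- 80% at n=20 needs SE 0.357, which lies inside the rounding range. The stated power is compatible with the printed figures but cannot be confirmed, as the individual data are not in the document.

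**Coding.** Under ±0.5 coding the interaction SE is twice the setup SE; under ±1 coding the two are equal. The printed ratio is 0.4/0.2 = 2, so I take ±0.5. Location benefit = main ± interaction/2:
- Interaction 1.0 dB: 1.0 ± 0.5 = 1.5 and 0.5 dB.
- Interaction 0.5 dB: 1.0 ± 0.25 = 1.25 and 0.75 dB.

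**Variances** (assuming one measure per cell and two beamformers in the reference model).
- Residual: σ² = 20 × 0.2² = 0.8. The interaction SE agrees: 20 × 0.4²/4 = 0.8.
- Beamformer slope: τ² = 20 × 0.4² − 0.8 = 2.4.

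**New trial, n=20, two sessions.**
- SE(main) = √((2.4 + 0.4)/20) = 0.374
- SE(interaction) = √(4 × 0.4/20) = 0.283
- SE(one location) = √((2.4 + 0.8)/20) = 0.400

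**Simulated probability of significance** (t tests, 19 df; a dash means not tabulated):

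| True benefits, sessions | Main | Interaction | Both | Main only | Weaker location |
|---|---|---|---|---|---|
| 1.5 / 0.5 dB, two | 72% | 92% | 66% | 6% | 22% |
| 1.25 / 0.75 dB, two | 72% | 39% | 28% | 44% | 43% |
| 2 / 0 dB, two | 72% | about 100% | 72% | 0% | – |
| 1.5 / 0.5 dB, one | 66% | 66% | 44% | 22% | 19% |
| 1.25 / 0.75 dB, one | 66% | 22% | 15% | 51% | – |

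Over the rounding of the standard errors, with two sessions, the share with both significant runs from 48% to 80% (interaction 1.0 dB) and from 17% to 50% (0.5 dB). With one measure per cell the ranges are about 26% to 69% and 9% to 27%.

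**Does the averaged test fit the null?** If I-BF and R-BF do not differ at either location, their average difference is zero. The beamformer term therefore tests the null as stated. Subjects with missing data are left out of the analysis concerned (section 9.3.7), so the cells stay balanced and the two locations are weighted equally.

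**Would a misleading average go unnoticed?** In the 2 / 0 dB case the planned interaction test is significant in nearly every trial. The two location estimates are then main ± interaction/2 from the same fit, with intervals from the same covariance matrix.

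**The case for a change.** The strongest argument for a change is that section 4 calls the trial confirmatory. If the location intervals and the wording of the conclusion are not fixed beforehand, they are chosen after the data are seen. The sentence in section 9.1 e that points to the beamformer effect justifies a sample size; it does not limit a claim. Under the 1.0 dB interaction, the main effect is significant while the weaker location is not in about 50% of trials.

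Part of this stands. A significant average is not evidence of benefit at each location, and a report that said otherwise would overreach. Three things keep it from being a fault in the plan.

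- The document makes no separate claim for each location. Side and behind can be read as the set of positions tested, and section 5 puts the beamformer data to product improvement and better use of an existing feature.
- The frequencies are not the plan's own. Only the effect sizes are. The variances come from one-decimal standard errors in a study about which section 9.1 c says: "While these test setups have always the talker in front". The equal 1.0 dB values are partly a construction, since the main effect was set to a minimum of interest while the interaction stayed at the average of the sources. In the sources themselves the benefits are 3.0 ± 0.8 = 3.8 and 2.2 dB, and 4.5 ± 0.25 = 4.75 and 4.25 dB: positive in both conditions.
- A formal location claim would gain little. The 95% interval at one location is about ±0.8 dB, and the weaker location reaches significance in only 22% or 43% of trials (two sessions).

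**Conclusion.** No change to the plan is needed. The sum-coded beamformer term is a valid test of the stated null and estimates the I-BF benefit averaged over 90 and 180 degrees, which is the effect the sample size was set for. The planned interaction test guards against the case that would mislead most, flagging a 2 versus 0 dB split in about 100% of trials. What is unwritten is how the two location estimates are shown and how the conclusion is worded when they differ. A competent analyst reports both estimates beside a significant interaction and words the main result as an average, and nothing in the plan prevents this.

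The chance that main effect and interaction are both significant spans roughly 9% to 80% across the scenarios, so no single figure should be quoted for it. All these probabilities assume ±0.5 coding, variances back-solved from rounded standard errors, independent test and retest residuals, and transfer of front-talker variances to side and back talkers. The conclusion does not depend on them: it rests on the match between the stated null and the planned test, and on the interaction being in the model with its own p-value.
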